Title	A multicenter trial of endoscopic radiofrequency ablation for macroscopically flat type high-grade and medium-grade intraepithelial squamous neoplasia using the Barrx™ Flex Radiofrequency Ablation System
Clinical Study Type	Prospective, multi-center, non-blinded, single-arm (non-randomized) post-market study
Product Name	Barrx™ Flex Radiofrequency Ablation System
Sponsor	Medtronic, Minimally Invasive Therapies Groups, Early Technologies
Local Sponsor	Medtronic MITG, Greater China 
Indication under investigation	Esophageal squamous cell neoplasia (ESCN)
Investigation Purpose	To measure the effectiveness and durability of the Barrx™ Flex Radiofrequency Ablation System in the eradication of diseased epithelium at 12 months post-treatment and up to 5 years in subjects with early flat-type -defined as type 0-IIb lesions on White Light Endoscopy (WLE) and Lugol's chromoendoscopy- esophageal squamous cell neoplasia (ESCN), defined as moderate-grade squamous intraepithelial neoplasia (MGIN) or high-grade squamous intraepithelial neoplasia (HGIN).
Product Status	The Barrx™ Flex Radiofrequency Ablation System obtained China Food and Drug Administration (CFDA) approval in January 2015 for use in China. The Barrx Flex System is indicated for the clinical treatment of lesions limited to the mucosa in the gastrointestinal tract, specifically flat intraepithelial neoplasia and Barrett's esophagus.
Primary Objective(s)	The primary objective is to measure the effectiveness of the Barrx™ Flex Radiofrequency Ablation System in the eradication of diseased epithelium at 12 months post-treatment in subjects with early flat-type -defined as type 0-IIb lesions on White Light Endoscopy (WLE) and Lugol's chromoendoscopy- esophageal squamous cell neoplasia (ESCN), defined as moderate-grade squamous intraepithelial neoplasia (MGIN) or high-grade squamous intraepithelial neoplasia (HGIN).

COVB3050540 (REACH) Clinical Investigation Plan

Version 7.0

15-Mar-2018

Page 10 of 62

Medtronic

Secondary Objective(s)	The secondary objectives are to assess safety, to measure durability of complete response during long-term follow-up, and to measure overall ESCC progression and associated mortality after treatment
Study Design	Multicenter, prospective cohort clinical trial in greater China. Patients will be followed-up for up to 5 years post initial RFA.
Sample Size	Up to 100 subjects will be included in the cohort, in up to 10 clinical sites. This is excluding up to 50 “run-in” subjects, defined as up to 5 patients for each endoscopist that is inexperienced with RFA or has had no onsite RFA training from CICAMS. Data from the run-in patients will be analyzed separately from the cohort.
Inclusion/Exclusion Criteria	Inclusion Criteria

Medtronic Confidential

	
 1. Patient is 18-85 years of age 2. Patient has evidence of ESCN, within the last 3 months, patient demonstrated a new diagnosis or a reconfirmed diagnosis of squamous MGIN or HGIN of the esophagus 3. On endoscopic examination, subject has at least one USL that measures at least 3 cm in at least one dimension and is greater than ¼ of the esophageal circumference and has MGIN or HGIN on biopsy, confirmed by central pathologist 4. All lesions in the esophagus are completely flat (Paris type 0-IIb), both on WLE and Lugol’s chromoendoscopy 5. The maximum allowable linear length of “USL-bearing esophagus” is 12 cm 6. Baseline endoscopic ultrasound (EUS) (if applicable) shows no exclusionary findings for the trial 7. Computed tomography (CT) scan of chest and upper third of the abdomen (if applicable) shows no exclusionary findings for the trial 8. Based on the judgment of the study endoscopist, the patient is eligible for treatment, and follow-up endoscopy and biopsy as required by the protocol 9. EMR or ESD occurred > 3 months before enrollment, patients may be eligible for the study if procedure was curative (negative margins and no risk of lymph node involvement) and the patient has no other findings concerning for cancer 10. The subject is willing to provide written, informed consent to participate in this clinical study and understands the responsibilities of trial participation 
Exclusion Criteria
 
 1. Patient has esophageal squamous cell carcinoma (ESCC) 2. Any non-flat (Paris type 0-I, 0-IIa, 0-IIc, 0-III) abnormalities anywhere in the esophagus 3. Any abnormalities under WLE, Lugol’s or NBI that are suspicious for ESCC anywhere in the esophagus (e.g. ‘pink sign’ USL, defined as a color change after Lugol’s staining: initially whitish yellow and pink 2-3 minutes later) 4. Any USL with MGIN or worse on biopsy outside the treatment area 5. Esophageal stricture preventing passage of a therapeutic endoscope 6. Prior endoscopic mucosal resection (EMR) or endoscopic submucosal dissection (ESD) which occurred < 3 months before enrollment.
--	--

	
 7. Any esophageal dilation in the past 12 months 8. Any history of a non-squamous cell cancer of the esophagus, or any history of a squamous cell cancer of the esophagus (any stage) 9. Any previous ablative therapy within the esophagus (photodynamic therapy, multipolar electrical coagulation, argon plasma coagulation, laser treatment, cryoablation, or other) or any radiation therapy to the esophagus. 10. Previous esophageal surgery, except fundoplication without complications (i.e., no slippage, dysphagia, etc.) 11. Evidence of esophageal varices detected within last 6 months or at initial RFA procedure 12. Patient has active reflux esophagitis grade C or D. 13. Evidence of eosinophilic esophagitis on endoscopy and/or histology 14. Inner diameter of the esophagus measuring less than 18mm 15. Report of uncontrolled coagulopathy with international normalized ratio (INR) > 2 or platelet count <75,000 platelets per μL (note: a complete blood count is not required for all subjects in this study) 16. Patient is using anti-thrombotic agents that cannot be discontinued 7 days before and after therapeutic sessions 17. Patient has an implantable pacing device (examples: automated implantable cardioverter defibrillator, neurostimulator, cardiac pacemaker) and has not received clearance for enrollment in this study by specialist responsible for the pacing device 18. Patient has life expectancy less than 5 years 19. Patient suffers from psychiatric or other illness and/or has a known history of unresolved drug or alcohol dependency that would limit ability to comprehend or follow instructions related to informed consent, post- treatment instructions, or follow-up guidelines 20. Patient is considered to be part of a vulnerable population (e.g. prisoners or those without sufficient mental capacity) 21. The subject has participated in an investigational drug or device research study within 30 days of enrollment that would interfere with this study 22. Patient is pregnant or has plans to become pregnant in the ensuing 12 months (confirmation of non-pregnant status in women of child-bearing age and ability required with urine or blood test to be eligible)

Study Procedures and Assessments
	
Subject’s duration of involvement expected to be up to 60 months. The overall study duration expected to last a total of 6 years.

Medtronic Confidential

First 12 months will be indicated as “treatment phase”.

Subject eligibility will be documented at a Baseline Qualifying Exam (BQE) as part of regular care. Eligible subjects will be consented and will undergo primary circumferential radiofrequency ablation (12J/cm² applied once with no cleaning of coagulum) within three months after BQE. All subjects will return 3, 6 and 9 months later for a repeat standardized chromoendoscopy. Flat USLs found within the previously treated area will be biopsied and treated again with RFA. Patients with ESCC in biopsies, non-flat visible lesions or lesions otherwise suspicious for ESCC (exceedance of initial inclusion criteria) found during follow-up will undergo escape treatment (see section 9.4.3 for description). If subsequent pathology assessment shows progression, defined as ESCC in any biopsy/resection specimen will be considered a failure of the primary endpoint. All subjects will return at 12 months after the primary RFA for biopsy to evaluate the primary endpoint of “complete response.”

Subsequent study duration after 12 months until 60 months will be defined as “follow-up phase.”

Patients with a complete response at 12 months will directly enter the follow-up phase, whereas patients with residual ESCN at 12 months (“treatment failures”) will undergo escape treatment per investigator’s discretion under the hospital standards of care.

The follow-up phase consists of yearly Lugol’s endoscopies with biopsies. If any flat USL will be found in TA, additional RFA treatment will be performed. If subsequent biopsies show MGIN or worse, an extra FU endoscopy will be performed within 3 months. A maximum of 4 consecutive RFA sessions are allowed and if CR won’t be re-established thereafter, escape-treatment will be indicated. Escape treatment is directly indicated for patients with ESCC in biopsies, non-flat lesions and lesions otherwise suspicious for ESCC (in line with the treatment phase) in TA.

Escape treatment may consist of endoscopic mucosal resection (EMR), endoscopic submucosal dissection (ESD), or non-endoscopic therapy such as surgery, radiotherapy or chemotherapy, at the discretion of the physician under the hospital standard of care. As long as pathology indicates endoscopic treatment (i.e.: sm1 disease, well/moderate differentiation, no lymphovascular infiltration and

	
negative vertical resection margins), trial participation will be continued.
 
All patients, regardless of failure of the primary endpoint or use of escape treatment during the trial, will be followed to study termination to assess secondary endpoints. A patient that has not been withdrawn or otherwise disqualified from the study, will have completed the study when the patient has finished all follow-up visits and the study has been terminated.

Safety Assessments	
Adverse events will be reported by number, severity, and relationship to the study procedures and devices.

Statistics	
The primary study hypothesis is that 80% of treated subjects will have a complete response at 12 months after the initial treatment session (per protocol analysis). Descriptive statistics will be used to summarize primary and secondary endpoints along with 95% confidence intervals or precisions as appropriate.

4. Introduction

4.1. Background

Esophageal cancer is the 9th most common cancer and the 6th most common cause of cancer death world-wide, with 442,000 new cases and 440,000 deaths in 2013 (1).

The incidence rate of esophageal cancer varies widely by region, with highest rates found in Eastern and Central Asia and Eastern and Southern Africa (1, 2). In China in 2011, esophageal cancer was the 4th leading cause of cancer death among both men and women, behind lung, liver, and stomach cancer (3).

In high-risk areas of Central Asia and North-Central China, esophageal squamous cell carcinoma (ESCC) represents 90% of esophageal cancer cases, compared to approximately 26% among Caucasians in the United States where esophageal adenocarcinoma is more common (2).

Risk factors for the development of ESCC include alcohol consumption, tobacco use, very hot drinks, and exposure to certain carcinogens found in salted vegetables and preserved fish (4, 5).

ESCC develops from the epithelial cells that line the esophagus. The precursor lesion to ESCC is esophageal squamous intraepithelial neoplasia (6, 7), also known as esophageal squamous cell neoplasia (ESCN), which is defined histologically as nuclear atypia (enlargement, pleomorphism and hyperchromasia), loss of normal cellular polarity, and abnormal tissue maturation (6).

Intraepithelial neoplasia is graded according to the proportion of the epithelial thickness that contains neoplasia (6). Lesions are categorized as either low-grade intraepithelial neoplasia (LGIN) or high-grade intraepithelial neoplasia (HGIN) depending on the extent of the neoplasia within the epithelium. In China where the incidence of ESCC is high, many pathologists adhere to a three-tier classification for intraepithelial squamous neoplasia, as shown below.

Table 1. Three-tier Classification for Intraepithelial Squamous Neoplasia

Class	Description
LGIN	Intraepithelial neoplasia confined to the lowest third of the epithelium (mild dysplasia)
MGIN	Intraepithelial neoplasia involving the lower two thirds of the epithelium (moderate dysplasia)
HGIN	Intraepithelial neoplasia involving all thirds of the epithelium (severe dysplasia)

Follow-up studies in China have shown that the rate of progression to ESCC differs significantly between the grades of intraepithelial neoplasia. At 3.5 years and 13.5 years, respectively, the progression rates were 5% and 24%, respectively for LGIN; 27% and 50% for MGIN; and 65% and 74% for HGIN (8, 9).

Once diagnosed, the prognosis for ESCC is often quite poor and depends on the stage of disease at diagnosis. Worldwide 5-year survival rates (2001-2007) have been estimated at 37%, 18%, and 3% for localized, regional, and distant disease, respectively (7, 10).

Thus, early screening and endoscopic treatment of MGIN and HGIN before the progression to ESCC may improve outcomes (11).

Management of ESCN commences with an extensive staging work-up, which typically includes chromoendoscopy, multiple biopsies of the esophagus with targeting of unstained lesions (USLs) on chromoendoscopy and any irregularities of the mucosa, endoscopic resection (ER) of any mucosal irregularity, and in some cases endoscopic ultrasound and computed tomography (CT) to rule out deeply invading lesions or metastatic cancer (12). Review of all histopathology is performed to determine the grade of neoplasia and the depth of invasion, when applicable.

Based on neoplastic progression rates, LGIN is generally managed with endoscopic surveillance and biopsies. Given the higher risk of progression to ESCC, patients with MGIN and HGIN are typically offered therapy. These therapies have consisted of wide-field endoscopic mucosal resection (EMR) or

endoscopic submucosal dissection (ESD), focal ablation, and surgical esophagectomy. Each intervention has specific risks and benefits that have been reported in the literature.

For wide-field EMR, resecting more than a 4 cm length of the esophagus or involving more than 50% of the inner circumference has a very high stricture rate, and the procedure is technically demanding. In addition, recurrence has been reported in up to 26% of cases (13).

ESD allows en bloc removal of neoplastic tissue regardless of length (13, 14). However, post-procedural side effects remain a challenge; strictures have been reported to complicate more than 90% of cases of esophageal ESD involving the entire lumen circumference, with resultant dysphagia requiring multiple sessions of dilations, with decrease in patients' quality of life. This procedure is even more technically demanding, requiring a high level of expertise, especially for large lesions. In addition, a long learning period is required to successfully perform ESD, and therefore this procedure can only be performed in high capacity institutions (15, 16).

Both EMR and ESD enable en bloc resection of neoplasia and allow for a pathological assessment to evaluate the curability (13-16).

Surgical esophagectomy is curative for ESCN, but the operative mortality at high-volume centers remains 3% or higher and the morbidity of the resulting gastric pull-up is substantial. Morbidity and mortality rates may even be higher for cases located in the upper 2/3 of the esophagus (17).

Radiofrequency ablation (RFA) is an endoscopically guided procedure which uniformly removes the diseased squamous epithelium without the need for removing the entire organ, as in surgery (11, 18, 19). RFA has been shown to safely, effectively, and durably eradicate early neoplasia in Barrett's esophagus, the precursor of esophageal adenocarcinoma (20-22). Several studies have demonstrated the potential of RFA to treat early ESCN as well (11, 19, 23-25). In a retrospective analysis of 65 patients with flat-type ESCN, RFA was also shown to provide similar effectiveness to ESD in the short-term treatment of ESCN, but with fewer adverse events, especially in lesions extending more than $\frac{3}{4}$ of the circumference (26).

This clinical study will assess (i) the effectiveness of radiofrequency ablation (RFA) using the Barrx™ Flex Radiofrequency Ablation System in the eradication of diseased epithelium at 12 months post-treatment, and (ii) the durability of established eradication of disease during 5 years of follow-up, in subjects with early ESCN, defined as MGIN or HGIN.

4.2. Purpose

To measure the effectiveness and durability of the Barrx™ Flex Radiofrequency Ablation System in the eradication of diseased epithelium at 12 months post-treatment and up to 5 years in subjects with early flat-type -defined as type 0-IIb lesions on White Light Endoscopy (WLE) and Lugol's chromoendoscopy-

esophageal squamous cell neoplasia (ESCN), defined as moderate-grade squamous intraepithelial neoplasia (MGIN) or high-grade squamous intraepithelial neoplasia (HGIN).

5. Objectives and Endpoints

5.1. Objectives

5.1.1. Primary Objective(s)

The primary objective is to measure the effectiveness of the Barrx™ Flex Radiofrequency Ablation System in the eradication of diseased epithelium at 12 months post-treatment in subjects with macroscopically flat-type – defined as Paris type 0-IIb on white light endoscopy (WLE) and Lugol's endoscopy- early esophageal squamous cell neoplasia (ESCN), defined as moderate-grade squamous intraepithelial neoplasia (MGIN) or high-grade squamous intraepithelial neoplasia (HGIN).

5.1.2. Secondary Objective(s)

The secondary objectives are to assess safety, to measure durability of complete response during long-term follow-up, and to measure overall ESCC progression and associated mortality after treatment.

5.2. Endpoints

5.2.1. Primary Endpoint

The percentage of subjects with “complete response (CR),” defined as complete eradication of squamous histological abnormalities (MGIN or worse) within the treatment area (TA) at 12 months after the initial treatment session (per protocol analysis). Patients who show ESCC in biopsies or resection samples are defined as failures for this endpoint, even if subsequent biopsies at 12 months indicate CR. The primary study hypothesis is that 80% of treated subjects will have a complete response.

Patients

All 100 patients who are included in the cohort will be assessed for the primary endpoint. The run-in patients will not be included for the primary endpoint analysis.

Biopsies

Only biopsies obtained from the original USL bearing portion of the esophagus (the treatment area) will be used in the analysis for the primary endpoint analysis. MGIN or worse noted in any biopsy from outside this region are not considered failures of ablation for the purposes of the primary endpoints.

5.2.2. Secondary Endpoint(s)

1. The percentage of subjects with a sustained CR during long-term follow-up, defined as patients with a CR at 12 months that sustained this absence of squamous abnormalities (MGIN or worse) during all subsequent FU endoscopies through 60 months.
2. Proportion of patients with CR after primary RFA, defined as absence of MGIN or worse in any of the biopsies from the treatment area, at the three month visit.
3. Proportion of patients demonstrating progression within the treatment area (TA), defined as detection of ESCC in biopsy or resection specimen at any time within the first 12 months.
4. Occurrence of serious adverse device effects (SADE) after RFA treatment.
5. Proportions of “run-in” subjects, are defined as the first 5 subjects enrolled per endoscopist that is inexperienced with RFA or has had no RFA onsite training from CICAMS, with a CR at 3 and 12 months after the initial treatment session, and with sustained CR during follow-up.
6. Proportion of patients with CR at 12 months who subsequently developed recurrent disease in TA, defined as MGIN or HGIN for patients with MGIN at baseline, and MGIN or HGIN for patients with HGIN at baseline.
7. Proportion of patients with CR at 12 months who subsequently developed progressive disease in TA, defined as ESCC in biopsy or resection specimen.
8. Durability after reiterative RFA, defined as proportion of patients with a CR at 12 months who sustain or re-establish CR upon reiterative RFA treatment sessions during FU.
9. Durability after additional endoscopic treatment, defined as proportion of patients with CR at 12 months who sustain or re-establish CR upon endoscopic treatment (RFA and eventually in combination with EMR or ESD) during FU.
10. Esophageal squamous cell cancer mortality.
11. Proportion of patients demonstrating MGIN or worse outside the TA during treatment phase or follow-up.

6. Study Design

This clinical study will evaluate a subject population having macroscopically flat type (type 0-IIb) esophageal lesions with histological evidence of MGIN or HGIN in biopsy specimens obtained from the esophagus.

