6.1. Duration

Enrollment of up to 100 subjects is expected to take 12 months. Subject’s duration of involvement in the study is expected to be up to 60 months (estimated based on primary RFA plus 12 months of treatment phase and 48 months of follow-up). The overall study is expected to last a total of 6 years if enrollment is completed in a timely manner.

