Although preliminary, results for the long-term follow-up of this study will be shortly discussed. Sustained CR during 5 years follow-up was observed in 86% (67/78 patients). Recurrence occurred in 9% (7/78 patients, MGIN 5, HGIN 1). 5 were managed with RFA, one with ESD. Progression of baseline disease occurred in another 5% (4/78 patients; HGIN (n=1), sm-ESCC (n=3)); all were treated with ESD. Two progressor lesions were normally stained after Lugol's and with repeatedly negative biopsies, and were therefore left untreated. Later both lesions were considered suspicious for cancer and escape treatment was performed, with pathology assessment for one case showed submucosal cancer buried under normal epithelial cells. Pathology assessment for the second case is pending.

However, protocol violations during follow-up occurred in the majority of patients (59%) resulting in prolonged follow-up intervals, lesions left untreated or no adequate follow-up after detection of recurrent or progressive disease. This might have interfered with the results, and those might have been better with strict follow-up protocols.

The 12 patients with residual ESCN suffered a poorer prognosis. Fifty-eight percent (7/12 patients) developed progressive disease and were treated with either ESD (n=2) or non-endoscopic treatment (n=5), suggesting that RFA failures should directly be managed with an alternative treatment like EMR or ESD.

Therefore, to further assess the safety, effectiveness, and durability of the Barrx™ Flex Radiofrequency Ablation System for the eradication of ESCN, the current study will employ methods similar to the 2 studies reported above but with a consistent primary RFA dose of 12 J/cm² with one application and no cleaning of the coagulum, and with subsequent 5-years follow-up according to strict study protocols.

7. Product Description

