9.10. Definitions

-CR = complete response

Absence of MGIN or worse in biopsies from TA at a single endoscopy.

- Escape treatment

Escape treatment is indicated for lesions with (i) ESCC in biopsies, (ii) non-flat lesions, or (iii) lesions otherwise suspicious for ESCC (e.g. pink-sign positive lesions). Escape treatment will be performed by investigator's distinction and per hospital's standards of care. Subsequent pathology assessment determines whether patient is defined as progressor and failure for the efficacy endpoint.

- Progressive disease

This term is applicable during the whole study. Progressive disease is defined as ESCC in any biopsy or resection specimen. Progressive disease on biopsy will always be treated with escape treatment.

Patients with progressive disease within the first 12 months are a failure for the primary efficacy endpoint, whereas progression patients in subsequent 4 years of follow-up are a failure for the durability endpoint. Progressive disease can be classified into 2 categories based on pathology:

- Eligible for endoscopic treatment, if all of the following characteristics are met: good to moderate differentiation, negative vertical resection margins, m1/m2/m3/sm1 disease and without lymphovascular infiltration.
- Exceeding the limits for endoscopic treatment, if any of the following characteristics was found: poor differentiation, positive vertical resection margins, sm-2 or sm-3 invasion or lymphovascular invasion.

- Treatment failure

This term is applicable to the first 12 months of study. All patients with residual ESCN at the 12 months endoscopy, and patients who progressed to ESCC before 12 months, will be defined as treatment failures.

- Sustained CR

This term is applicable during follow-up, to all patients that were not defined as treatment failures at 12 months. Sustained CR is defined as sustained eradication of MGIN or worse in biopsies from TA, during all FU endoscopies until 60 months.

- Recurrent disease

This term is applicable during follow-up, to all patients that were not defined as treatment failures at 12 months. Recurrent disease is defined as flat (Paris type 0-IIb) USLs with MGIN or HGIN in biopsies from TA during FU, independent of baseline pathology. Recurrent disease will be treated with RFA initially, or escape treatment if persistent, as described in section 9.4.3

10. Risks and Benefits

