13.2. Sample Size Determination

The proposed sample size of up to 100 subjects is considered adequate for the study objective. From published data, a complete response rate of 80%-90% of the RFA treatment is expected at 12 months post-treatment for the subject population (18). With 100 study subjects, a precision (half 95% CI width) of 6%-8% will be achieved for estimating the primary endpoint of complete response rate. For safety, a sample of 100 subjects will have greater than a 99% chance to detect a rare event of 5% incidence or an 85% chance to detect a rare event of 2% incidence. The NIH defines an acceptable dropout rate at 20% or less. However, over 70% of all high-quality clinical studies in China had a dropout rate lower than 10%. For example, the dropout rate at CICAMS was 3% in a previous ESCN study.

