7.9.2. Secondary Endpoint(s)

1. The percentage of subjects with a sustained CR during long-term follow-up, defined as patients with a CR at 12 months that sustained this absence of squamous abnormalities (MGIN or worse) during all subsequent FU endoscopies through 60 months.
2. Proportion of patients with CR after primary RFA, defined as absence of MGIN or worse in any of the biopsies from the treatment area, at the three month visit.
3. Proportion of patients demonstrating progression within the treatment area (TA), defined as detection of ESCC in biopsy or resection specimen at any time within the first 12 months.
4. Occurrence of serious adverse device effects (SADE) after RFA treatment.
5. Proportions of "run-in" subjects, defined as the first 5 subjects enrolled per endoscopist, with a CR at 3 and 12 months after the initial treatment session, and with sustained CR during follow-up.

This document is electronically controlled. Printed copies are considered uncontrolled.

Confidential

12JUL2017

6. Proportion of patients with CR at 12 months who subsequently developed recurrent disease in TA, defined as MGIN or HGIN for patients with MGIN at baseline, and MGIN or HGIN for patients with HGIN at baseline.
7. Proportion of patients with CR at 12 months who subsequently developed progressive disease in TA, defined as ESCC in biopsy or resection specimen.
8. Durability after reiterative RFA, defined as proportion of patients with a CR at 12 months who sustain or re-establish CR upon reiterative RFA treatment sessions during FU.
9. Durability after additional endoscopic treatment, defined as proportion of patients with CR at 12 months who sustain or re-establish CR upon endoscopic treatment (RFA and eventually in combination with EMR or ESD) during FU.
10. Esophageal squamous cell cancer mortality.
11. Proportion of patients demonstrating MGIN or worse outside the TA during treatment phase or follow-up.

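### Sustained CR through 60 months is a simple proportion with no main rule for responders who miss visits, withdraw or die, so its value depends on an unstated counting choice

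*Protocol*

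**What the plan says.** Durability of complete response is a stated secondary objective (protocol 5.1.2, SAP 4.2). Its first-listed endpoint in protocol 5.2.2 is the percentage of 12-month responders who "sustained this absence of squamous abnormalities (MGIN or worse) during all subsequent FU endoscopies through 60 months". SAP 7.9.2 repeats this definition, with the condition applying "during all subsequent FU endoscopies through 60 months", and adds no estimator or denominator rule. Protocol 9.10 gives a similar definition: "Sustained CR is defined as sustained eradication of MGIN or worse in biopsies from TA, during all FU endoscopies until 60 months".

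Endpoints 6 (recurrence) and 7 (progression) are also proportions of 12-month responders over the same period, as are the durability endpoints 8 and 9. Endpoint 10, ESCC mortality, is named without a summary measure.

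Protocol 6.1 gives each subject's involvement as "primary RFA plus 12 months of treatment phase and 48 months of follow-up". The synopsis states: "The follow-up phase consists of yearly Lugol’s endoscopies with biopsies".

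On incomplete follow-up, SAP 7.4 (repeated in SAP 7.11 and protocol 13.6) commits to tabulating visit compliance and withdrawals with reasons. It also commits to a sensitivity analysis for missing data. The methods listed (last observation carried forward, multiple imputation, tipping point) are ones the analysis may use where appropriate. The per-protocol set in protocol 13.3 and SAP 7.1.3 is defined for the primary analysis. No time-to-event or censoring method appears in either document.

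**The concern.** A proportion over four years needs a decision on each responder who was clear when last examined but has no month-60 endoscopy. There are three choices: count the responder as sustained, exclude the responder, or count a failure. The text leaves all three open. If *all* endoscopies means all that were scheduled, an incomplete responder fails the definition. If it means all that were attended, the same responder succeeds. Last observation carried forward, the first sensitivity method listed, also counts that responder as a success.

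The promised sensitivity analysis does not settle this, because there is no fixed main analysis for it to test. The rule could be chosen after the pattern of loss is known. The 5-year durability figure, which is the reason for following subjects beyond month 12, would then reflect that choice as well as the disease.

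**Working it through.** **The plan's own figure.** Protocol 13.2 states: "With 100 study subjects, a precision (half 95% CI width) of 6%-8% will be achieved for estimating the primary endpoint of complete response rate". The Wald half-width 1.96 × √(p(1−p)/100) is 7.84 points at p = 0.80 and 5.88 points at p = 0.90, so the statement reproduces. It covers the 12-month endpoint only. No precision is given for sustained CR.

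**Inputs.**
- Responders at month 12: 80 to 90, from the expected CR of 80%–90% in 100 subjects (protocol 13.2).
- True sustained CR: S = 67/78 = 85.9%, from the earlier cohort in protocol 6.2. This is an assumption for the present trial.
- Follow-up: 4 years (protocol 6.1).
- Total loss D after month 12: 3%, 10% or 20%. Protocol 13.2 quotes these dropout figures (the 10% and 20% as upper limits) without a period. Applying them to months 12–60 is an assumption.

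**Model.** Constant hazards, with loss unrelated to recurrence:
- failure hazard h = −ln(67/78)/4 = 0.0380 per year
- loss hazard d = −ln(1−D)/4
- failures observed e = h/(h+d) × (1 − exp(−4(h+d)))
- clear at month 60 s = exp(−4(h+d))
- lost while clear l = 1 − e − s

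| D | d | e | s | l |
|---|---|---|---|---|
| 3% | 0.0076 | 0.139 | 0.833 | 0.028 |
| 10% | 0.0263 | 0.134 | 0.773 | 0.093 |
| 20% | 0.0558 | 0.127 | 0.687 | 0.186 |

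**Result under each counting rule.**

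| Rule | D = 3% | D = 10% | D = 20% |
|---|---|---|---|
| Lost counted as sustained, s + l | 86.1% | 86.6% | 87.3% |
| Lost excluded, observed failures kept, s/(s + e) | 85.7% | 85.2% | 84.4% |
| Lost counted as failures, s | 83.3% | 77.3% | 68.7% |
| Kaplan-Meier or life table | 85.9% | 85.9% | 85.9% |

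A version with loss and recurrence resolved at four annual visits gives nearly the same values: 86.2/86.8/87.7%, 85.8/85.4/84.8% and 83.3/77.3/68.7%.

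**Against sampling error.** The half-width at S = 85.9% is 1.96 × √(0.859 × 0.141/n), which is 7.6 points for n = 80 and 7.2 points for n = 90. The first two rules stay within about 1.5 points of 85.9% even at 20% loss. Counting losses as failures gives s = S(1−D), a bias of S × D: 2.6, 8.6 and 17.2 points. That bias passes the half-width once D exceeds 7.2/85.9 = 8.4% (n = 90) or 7.6/85.9 = 8.8% (n = 80).

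**The case against.** The documents are not silent on loss. SAP 7.4 is devoted to missing data and dropouts, commits to a sensitivity analysis and names candidate methods. Protocol 9.9 sets out tracing steps before a subject is declared lost, and all subjects are followed whatever their primary-endpoint result or escape treatment. The study is single-arm and descriptive with no durability hypothesis, so a proportion is a legitimate summary. At the 3% dropout quoted for the lead site, every rule lies within 2.6 points of the assumed truth. The large discrepancy arises only when losses count as failures, which neither document proposes. Kaplan-Meier is itself biased if loss is related to recurrence.

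Most of this stands, and it limits the point. A reader might infer several stronger things that the documents do not support:
- **That the plan makes no allowance for loss.** It makes a general one; what is missing is a main rule for this endpoint.
- **That 59% of the earlier cohort dropped out.** Protocol 6.2 reports follow-up protocol violations in 59%: long intervals, untreated lesions, or inadequate follow-up after disease was found. That is not a dropout rate.
- **That eligibility to age 85 implies many deaths.** Exclusion 18 removes patients with life expectancy under 5 years.
- **That 3%–10% is lost each year.** No quoted figure is stated to be annual, and these rates would mean 1 − 0.97⁴ = 11% to 1 − 0.90⁴ = 34% in total. The upper end exceeds every dropout figure quoted.
- **That no proportion can approximate 5-year durability.** Two of the three rules come close when loss is non-informative.

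The objection does not supply the missing rule. A literal reading of the definition still permits counting losses as failures.

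**Conclusion.** The point holds as a gap in the analysis of a secondary endpoint, and it should be corrected. Sustained CR, with endpoints 6 and 7, has no main rule for incomplete follow-up. Between the extreme rules the same data give results 2.8, 9.3 or 18.6 points apart at total loss of 3%, 10% or 20%. At 10% or more that exceeds the sampling half-width of 7.2 to 7.6 points. Nearly all of the spread comes from counting losses as failures.

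These sizes rest on a true value of 67/78, constant hazard, non-informative loss, and the quoted dropout figures read as total loss over months 12–60. The documents do not say whether 67/78 already excludes lost subjects. Informative loss would change every row, including Kaplan-Meier.

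**What to change.** Amend SAP 7.9.2 as follows:

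1. Among 12-month responders, estimate sustained CR at 24, 36, 48 and 60 months by Kaplan-Meier or life table from the 12-month visit, with 95% confidence intervals. Censor at the last endoscopy with biopsy. An interval-censored estimate is an alternative, since disease is detected only at visits.
2. Estimate recurrence, progression and ESCC mortality by cumulative incidence, with death from other causes as a competing event. State how such deaths are treated for sustained CR, so that the results reconcile.
3. Keep the raw proportion as a supporting line with a stated denominator, and say how a missed intermediate visit is handled.
4. Fix two sensitivity analyses for this endpoint: missing counted as failure, and a tipping-point analysis.

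The cost is SAP wording and slightly more analysis work with standard procedures; no new data are needed. The main limitation is that Kaplan-Meier assumes loss is unrelated to recurrence, which is why item 4 should be fixed in advance.
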